#### **Specific Guidance on Transitioning from Oral to Injectable Phases**

Any grade 3 clinical or laboratory AE observed prior to Week 5 will prompt consultation with the CMC prior to any injectable dosing.

Grade 3 adverse events deemed after CMC consultation to clearly not be related to study product may be permissible to continue to injectable dosing provided

- a) Documented resolution to  $\leq$  Grade 1 prior to injectable dosing, and
- b) Approval of the CMC.

Grade 3 adverse events deemed related to study product, or any Grade 4 adverse event will lead to study discontinuation prior to injectable dosing. AE's will be followed until resolution in consultation with the CMC.

## General Criteria for Discontinuation of Study Product

Participants may voluntarily discontinue the study products for any reason at any time. Investigators will permanently discontinue participants from study product per protocol for any of the specific criteria below, which may be further clarified in the SSP Manual. Investigators also may permanently discontinue participants for reasons not shown here or in the SSP Manual (e.g., to protect participants' safety and/or if participants are unable or unwilling to comply with study product use procedures). In such cases, the IoR or designee must first query the CMC for review. The CMC will provide a written response to the site indicating whether the CMC has recommended permanent discontinuation of study product based on careful review of all relevant data. It should be noted that the safety of the participant should always take precedence, and therefore, an IoR may determine that study product be permanently discontinued before the CMC has time to respond. This is acceptable, and in such cases, the CMC should be notified as soon as possible regarding the nature of the case and the course of action taken.

The criteria for permanent discontinuation of study product use for an individual participant are:

- Study product-related toxicity requiring permanent discontinuation of study product per the guidelines above and below
- Completion of regimen as defined in the protocol
- Request by participant to terminate study product
- Clinical reasons determined by the IoR
- Acquires HIV infection or hepatitis B virus (HBV) infection
- Pregnancy or expresses a desire to become pregnant

Participants in the injection phase who prematurely and permanently discontinue study product should be asked to continue to be followed according to the applicable Schedule of Evaluations and Procedures (Appendices I, II or III).

Study product will be temporarily withheld from a participant for any of the following reasons:

- Report of use of prohibited concomitant medications as described in the SSP Manual. Study
  product use may resume upon consultation with the CMC and when the participant reports
  that he/she is no longer taking the prohibited medication, provided other reasons for
  temporary study product hold/permanent discontinuation do not apply. The CMC should be
  consulted in all cases where a participant reports taking a prohibited product during the
  course of the study.
- The participant is unable or unwilling to comply with required study procedures such as HIV testing and routine laboratory assessments, or otherwise might be put at undue risk to their safety and well-being by continuing study product use, according to the judgment of the IoR. The IoR must consult the CMC on all temporary study product holds instituted for this reason for further guidance on resuming study product use, continuing the temporary hold, or progressing to permanent discontinuation.

• The participant has one or more reactive HIV test results, or expresses a concern about having acute HIV infection. Criteria for resuming use of study product in these circumstances are defined in the SSP Manual and Section 5.17 of the protocol.

Participants who temporarily or permanently discontinue study product during the oral phase will be instructed to return all study products as soon as possible.

# Nausea, Vomiting, and Diarrhea

CONDITION AND SEVERITY 	IMMEDIATE ACTION	FOLLOW-UP AND MANAGEMENT 					
	Nausea, Vomiting, and Diarrhea						
Grade 1 and 2	Continue study product (reminder to take study product with food)	Treat symptomatically with hydration, oral antiemetic therapies or antiemetic suppositories at the discretion of the Investigator. The Investigator should order any clinically relevant laboratory analyses (per judgment of the Investigator).					
Grade ≥ 3	Discontinue study product temporarily	Participants with Grade $\geq 3$ nausea, vomiting, or diarrhea, for which an alternative etiology is not established, must discontinue the study product temporarily until Grade 2 or lower and be treated symptomatically. Should condition(s) not improve to Grade $\leq 2$ within 7 days, the Investigator should consult the CMC for guidance on continuing the temporary discontinuation or progressing to permanent discontinuation of study product.					

# AST/ALT

CONDITION AND SEVERITY 	STUDY PRODUCT USE	FOLLOW-UP AND MANAGEMENT 
(New clinic		S in AST/ALT rom baseline clinical finding only)
Grade 1	Continue study product unless participant is symptomatic	AST/ALT must be repeated every 4 weeks until they are < Grade 1. Study product may be continued while repeating AST and ALT at the discretion of the investigator provided the participant is asymptomatic. In the case of symptomatic participants, study product will be held temporarily, and management (including resumption of study product) should be arranged in consultation with the CMC.
Grade 2*	Discontinue study product temporarily	Study product should be temporarily held for any Grade 2 AST/ALT. Participants should have AST/ALT re-checked as soon as possible (ideally within 1 week of the receipt of the results) and then be followed weekly until levels are Grade ≤ 1. The frequency of follow up may be altered at the discretion of the site investigator following consultation with the CMC. Resumption of study product should be arranged in consultation with the CMC. In the case of symptomatic participants, study product will be held temporarily, and management (including resumption of study product) should be arranged in consultation with the CMC.
*ALT ≥3xULN and bilirubin ≥2xULN	Permanently discontinue study product	Study product should be permanently discontinued for any ALT $\geq$ 3xULN with associated bilirubin $\geq$ 2x ULN and the CMC should be immediately notified (see Section 6.4.2. regarding additional reporting requirements related to abnormalities in these values). Participants should have AST/ALT re-checked as soon as possible (at most within 1 week of the receipt of the results). Participants should then be followed weekly until levels are Grade $\leq$ 1 unless indicated by the CMC.

# AST/ALT (Cont'd)

CONDITION AND SEVERITY 	STUDY PRODUCT USE	FOLLOW-UP AND MANAGEMENT 
(N		EVATIONS in AST/ALT increase from baseline clinical finding only)
Grade 3 and 4	Permanently discontinue study product	Study product should be permanently discontinued for any Grade 3 or 4 AST/ALT and the CMC should be immediately notified. Participants should have AST/ALT re-checked as soon as possible (at most within 1 week of the receipt of the results). Participants should then be followed weekly until levels are Grade ≤ 1 unless otherwise indicated by the CMC.  Participants should continue to be followed on study/off product, following the appropriate Schedule of Evaluations (based on number of injections received).

Note for all grades: All study participants will be negative for HBsAg at study entry, and that participants who enter the study without evidence of immunity to HBV will be referred for HBV vaccination. Therefore, pre-existing HBV infection is not likely to be a cause of AST/ALT elevations.

Careful assessments should be done to rule out the use of alcohol, lactic acidosis syndrome, non-study medication-related product toxicity, herbal medications/supplements, or viral hepatitis as the cause of elevation in AST or ALT of any grade. The participant must be carefully assessed for any symptoms or signs of hepatotoxicity, including fatigue, malaise, anorexia and nausea, jaundice, acholic stools, right upper quadrant pain, or hepatomegaly. If the AST/ALT elevation is considered most likely to be due to concomitant illness or medication, standard management, including discontinuation of the likely causative agent, if possible, should be undertaken. If symptoms or signs of clinical hepatitis are present, study product must be held or discontinued. In addition, all participants with elevated values should be considered for testing for Hepatitis A, B, and C infection.

# Creatinine Clearance

CONDITION AND SEVERITY 	STUDY PRODUCT USE	FOLLOW-UP AND MANAGEMENT 			
CREATININE CLEARANCE					
Estimated CrCl< 50 mL/min	Discontinue study product temporarily	If the calculated creatinine clearance is <50mL/min, it should be confirmed within 1 week of the receipt of the results, and the CMC should be consulted			
Confirmed CrCl< 50 mL/min	Permanently discontinue study product	If the calculated creatinine clearance is confirmed to be <50 mL/min, the study product must be permanently discontinued and the CMC notified. Participants who fail to have a confirmed test within 2 weeks of receiving the initial result, should be permanently discontinued from use of the study product and the CMC is notified.			
Re-testing result is ≥50 mL/min	Consult CMC for guidance	If re-testing yields a result ≥ 50 mL/min, the Investigator must consult the CMC for further guidance on resuming study product use, continuing the hold temporarily, or progressing to permanent discontinuation.  If the investigator in consultation with the CMC has determined that the case has stabilized, it may be possible to decrease the frequency of follow-up laboratory testing in addition to resumption of study product.			

# Creatine Phosphokinase (CK or CPK)

CONDITION AND SEVERITY 	STUDY PRODUCT USE	FOLLOW-UP AND MANAGEMENT 	
Creatine Phosphokinase			
Grade 3	Continue study product until repeat test results are available	A Grade 3 or higher elevation in CPK should result in a repeat assessment within 2-4 weeks to ensure the result is transient or due to exercise and will not require a change in study treatment. A history regarding use of products known to cause increase of CPK (such as statins) physical activity or exercise preceding the CPK evaluation should be obtained.	
Grade 4	Continue study product until repeat test results are available if the elevation is thought to be possibly or probably related to study product.	Grade 4 elevations in CPK should have a repeat assessment after the subject has abstained from exercise for >24 hours. For persistent Grade 4 CPK elevations that are considered possibly or probably related to the study product, study product should be discontinued and the participant should be followed on study/off study product.	

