# 5.15 Procedures for Participants Who Do Not Complete the Full Course of Injections

Participants who received the Week 5 (Injection #1) and Week 17 (Injection #2) injections but will not receive the final injection (Injection #3) will be followed for 52 weeks after their Week 17 injection, through to Week 69. Because participants meeting these criteria received an injection at Week 5 and Week 17, the procedures for Weeks 6, 9, 13, 18, and 23 Safety Visits as outlined above and in the Schedule of Evaluations and Procedures will remain the same. Procedures for subsequent study visits for these participants are outlined in Appendix II.

Participants who received the Week 5 injection (Injection #1) and will not receive the next two injections will be followed for 52 weeks after their Week 5 injection, through to Week 57. Because participants meeting these criteria received an injection at Week 5, the procedures for Weeks 6, 9, and 13 Safety Visits as outlined above and in all Schedule of Evaluations and Procedures will remain the same. Procedures for subsequent visits for these participants are outlined in Appendix III.

Participants who are unable to receive the first injection for any reason will be terminated from the study. If the reason is due to HIV infection or pregnancy, refer to Section 5.17 and 5.19, respectively.

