#### APPENDIX VI: TOXICITY MANAGEMENT

## **Toxicity Management General Guidance**

In general, the IoR has the discretion to hold study product at any time if she/he feels that continued product use would be harmful to the participant, or interfere with treatment deemed clinically necessary according to the judgment of the IoR. In addition, a Clinical Management Committee (CMC) will be established for this study. The CMC's responsibilities will include consultation and decision-making regarding management of toxicities and study product administration, including product resumption following the occurrence of certain types of toxicities and/or permanent discontinuation. Throughout this appendix are examples of AEs that require consultation with the CMC; in all such cases, the CMC should be notified as soon as possible and ideally within 72 hours of site awareness of the AE in question. Investigators also should consult the CMC for further guidance in restarting study product or progressing to permanent discontinuation. Revealing a participant's blinded status will occur only for individuals who become HIV infected and choose to initiate antiretroviral therapy. (A full description of the CMC's role and responsibilities is included in the SSP Manual).

#### Grade 1 or 2

In general, participants who develop a Grade 1 or 2 AE regardless of relatedness to study product, and that is not specifically addressed in the Table below may continue use of the study product per protocol.

#### Grade 3

Participants who develop a Grade 3 AE or toxicity that is not specifically addressed in the Table below and is judged to be related to study product by the Investigator, study product use should be temporarily discontinued in consultation with the CMC. In general, and unless otherwise decided in consultation with the CMC, the investigator should re-evaluate the participant until resolution of the toxicity. The study product should be permanently discontinued if improvement to severity  $\leq$  Grade 2 cannot be documented within 4 weeks of receipt of the initial result. If study product is resumed and the same Grade 3 AE recurs at any time, the Investigator must consult the CMC for further guidance on holding of study product, frequency of reevaluation or progression to permanent discontinuation of the study product.

#### Grade 4

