Participants who develop a Grade 4 AE or toxicity that is not specifically addressed below (regardless of relationship to study product) should have the study product temporarily discontinued. The Investigator must consult the CMC and continue the temporary study product hold until a recommendation is obtained from the CMC. In general, study product use will not be resumed if the Grade 4 AE is considered related to study product use. If, in consultation with the CMC, study product use is resumed and the same Grade 4 AE recurs at Grade 4 level at any time, study product must then be permanently discontinued.

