# **Guidance for Allergic Reactions**

Participants may continue to receive oral or injectable study product for Grade 1 or 2 allergic reactions at the discretion of the IoR or designee. The participant should be advised to contact the study site staff immediately if there is any worsening of symptoms or if further systemic signs or symptoms develop. Antihistamines, topical corticosteroids, or antipruritic agents may be prescribed.

Participants with Grade  $\geq 3$  allergic reactions that are considered to be related to study product should permanently discontinue study product and continue to be followed on study/off study product. Participants should be treated as clinically appropriate and followed until resolution of the AE.

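### The Grade 4 CPK rule makes suspected drug-relatedness the condition for continuing product, states no action for an unrelated elevation, and does not require the repeat result before the next injection

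*Protocol*

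**What the plan says.** The CPK table in Appendix VI of the protocol has one row for Grade 3 and one for Grade 4.

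- **Grade 3, product use:** continue until the repeat result is back, with no condition on relatedness. The follow-up column asks for a repeat within 2-4 weeks and words this for elevations of Grade 3 or higher.
- **Grade 4, product use:** "Continue study product until repeat test results are available if the elevation is thought to be possibly or probably related to study product".
- **Grade 4, follow-up:** every such elevation is repeated after more than 24 hours without exercise. The only product action is for persistent cases, namely those "considered possibly or probably related to the study product, study product should be discontinued and the participant should be followed on study/off study product".

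Three other parts of Appendix VI bear on the point.

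- The general Grade 4 rule holds product whatever the relatedness, but only for events that the appendix does not address specifically. It adds that, in general, "study product use will not be resumed if the Grade 4 AE is considered related to study product use".
- The guidance on moving from the oral to the injectable phase says "Grade 3 adverse events deemed related to study product, or any Grade 4 adverse event will lead to study discontinuation prior to injectable dosing".
- The opening guidance says "the IoR has the discretion to hold study product at any time" if continued use is felt to be harmful.

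Sections 5.4, 5.6 and 5.8 require the scheduled Week 4, 13 and 23 results, respectively, to be reviewed before the next injection. None of them mentions a repeat test.

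**The concern.** A product-use rule that turns on relatedness should be at least as cautious when the drug is suspected as when it is not. Read literally, this cell does the opposite: suspicion of the drug is what permits continuation. The other branch is blank, so a site has to supply its own rule for an elevation it attributes to, say, exercise.

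The stake is participant safety and uniform handling across sites. The long-acting product cannot be withdrawn once injected. Section 1.2.4 reports drug detectable in plasma for up to 48 weeks after a single injection. Appendix V records rhabdomyolysis in the labelling of another integrase inhibitor, although none had been seen with this drug. An injection given while a Grade 4 CPK still awaits its repeat is therefore the case to guard against.

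**Working it through.** The protocol has no figure to reproduce here. The check sets the rules side by side and then works out the timing.

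**Step 1. Product action while the repeat is awaited, injection phase.**

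| Reading | Thought related | Thought unrelated |
|---|---|---|
| CPK cell as written | Continue | Nothing stated |
| Gap filled by the general Grade 4 rule | Continue | Hold and consult the CMC |
| Gap filled by inference (if related continues, unrelated does too) | Continue | Continue |

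The second reading reverses the safety ordering. The third removes the reversal but makes the cell's condition redundant, because product continues either way. No reading makes the related case the more cautious one, and the text does not choose between them.

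**Step 2. Once the repeat is back.** Persistent and related: discontinue. The table states no product action for an elevation that is persistent but unrelated. The repeat itself is required for every Grade 4 elevation, so the gap concerns product use and not monitoring.

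**Step 3. Can the repeat still be outstanding at an injection?** Inputs: injections at Weeks 5, 17 and 29; safety-visit chemistry, which includes CPK (Section 9.1), at Weeks 6, 9, 13, 18 and 23 between injections. Assumption: the 2-4 week interval, worded for Grade 3 or higher, applies to Grade 4 and runs from the draw.

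Repeat window = draw week + 2 to draw week + 4.

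- Week 6: 8 to 10, before Week 17
- Week 9: 11 to 13, before Week 17
- **Week 13: 15 to 17, reaching the Week 17 injection**
- Week 18: 20 to 22, before Week 29
- Week 23: 25 to 27, before Week 29

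Week 13 is the exposed safety visit. Section 5.6 requires review of the scheduled Week 13 result before the second injection, and that requirement is met while the repeat is pending. If the interval runs from receipt of the result, every window moves later by the laboratory turnaround. If the Grade 4 row is read as allowing a repeat soon after 24 hours' rest, the overlap disappears.

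**Step 4. Oral phase.** Section 6.3 counts abnormal laboratory findings as adverse events, so a Grade 4 CPK at Week 2 or 4 falls under the transition rule. Tablets are taken for 4 weeks, and Week 4 is the post-oral visit followed by washout. A Week 4 result therefore leaves no tablets to continue or hold. Only the Week 2 draw can affect ongoing tablets, for the remaining 4 - 2 = 2 weeks.

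**The case against.** The best defence is that the authors meant sites could await the repeat even when the drug is suspected. The Grade 3 row already continues product pending a repeat. Appendix V describes the CPK elevations seen so far as transient, without symptoms and mostly linked to exercise. The general rules yield to a specific table, so a difference from them is not in itself an error. This makes a policy of waiting defensible, and it stands to that extent. It does not rescue the wording: the cell sets a condition rather than granting a permission, and the unrelated branch is absent on either view.

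A reader might go further and infer that the CPK table and the transition rule are in open conflict, so that a site could choose between ending participation and giving a first injection, with consequences for who enters the primary analysis. The documents do not support that. The transition rule is headed as specific guidance, covers any Grade 4 event, and lacks the exception written into the general Grade 4 rule. Section 5.15 then says "Participants who are unable to receive the first injection for any reason will be terminated from the study". Its most natural reading is that it governs before Week 5. All that is missing is a cross-reference.

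The column headings carry footnotes whose text was not available, and the appendix says the discontinuation criteria may be clarified further in the SSP Manual. Either could already settle the point for sites.

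**Conclusion.** The Grade 4 CPK product-use cell is wrong as written. It ties continuation to suspected relatedness and leaves the unrelated case without an instruction. If the general Grade 4 rule fills the gap, the drug-related case is treated more permissively than the unrelated one. No provision requires the repeat before an injection, and the Week 17 injection is exposed if the 2-4 week interval applies to Grade 4.

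The point is minor. The protocol gives no Grade 4 CPK rate and reports no discontinuation for CPK, so the number of participants affected cannot be estimated. After the first injection, product is given only at Weeks 17 and 29. The investigator may hold product at any time, and before Week 5 the transition rule already bars injection. A reader might infer a routine hazard to participants; these limits do not support one. The conclusion rests on the protocol text alone, without the SSP Manual or the table footnotes.

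**What to change.** Reword the Grade 4 product-use cell so that both branches are stated and the related case is never the more permissive. For example: *Possibly or probably related: give no further product until the repeat CPK has been reviewed. Not related: continue while the repeat is awaited.* Holding in the related case is a clinical choice for the team to confirm. If they prefer to await the repeat in both cases, the cell should say so without a relatedness condition.

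Add to the same row: *The repeat CPK must be available and reviewed before any further injection.* Add a cross-reference in the CPK table that, before Week 5, the transition rule for any Grade 4 event governs.

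The cost is two or three sentences by clarification memo or amendment, and an occasional short hold or delayed injection. An injection moved outside its visit window needs CMC consultation under Section 5.13. The Grade 4 row itself asks only for more than 24 hours without exercise, so an early repeat would usually avoid the delay.
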